### 4.6 BENEFIT RISK ASSESSMENT

Severe CRS is an anticipated risk due to release of cytokines following T-cell activation. Anemia, leukopenia, and thrombocytopenia are other anticipated risks that commonly occur during treatment for hematologic malignancies. The safety monitoring and risk mitigation plan includes the following measures:

- Systematic premedication with dexamethasone and montelukast will be provided starting with the first dose of SAR440234 tested.
- Treatment with tocilizumab will be started if CRS Grade 2 is diagnosed. Two doses of tocilizumab will be available on site for each patient under treatment.
- A conservative MABEL approach is planned to define a very low dose as the starting dose in humans.
- Careful intra-patient dose escalation with conservative increases for each dose level will be performed. The dose escalation cohort will be initiated at a lower dose at the first infusion in each patient. The purpose of this design is to minimize exposure to sub-therapeutic doses while maintaining patient safety, particularly in the context when the FIH starting dose is very low. This strategy will facilitate rapid attainment of active therapeutic doses.
- Extensive clinical monitoring will be conducted during the Dose Escalation Part, including frequent assessment of vital signs during infusion and at specific time points post infusion. During Cycle 1 and the first 2 doses of Cycle 2 in the Dose Escalation Part, patients will

be hospitalized for the duration of each SAR440234 infusion (1 to 19 hours) and for the first 72 hours after the infusion is completed. During Cycle 1 and the first 2 infusions of Cycle 2 in the Expansion Part, patients will be hospitalized for the duration of the SAR440234 infusion (1 to 19 hours), and for 72 hours after completion of each infusion. During the remaining infusions of Cycle 2 and beyond in the Expansion Part, if the patient has tolerated the SAR440234 infusion well, the patient will be hospitalized only for the duration of each subsequent infusion (1 to 19 hours). The 2014 NCI Consensus Guidelines will be used to grade and guide the management of CRS (Appendix H).

- A DLT observation period of 42 days from the first administration of IMP in the first cycle, with administration of IMP on Day 1, Day 4 (DL ≥3), Day 8, and weekly thereafter, including at least 3 maximal subsequent doses in each dose level, will be followed to monitor for delayed effects of SAR440234 and for effects that occur only after the highest dose in Cycle 1.
- Continuous monitoring of vital signs will be implemented if CRS Grade ≥2 develops; blood chemistry will be tested every 8 hours. Any patients with Grade 2 or greater CRS must be admitted to the ICU.
- During the first cycle, patients will be monitored every 8 hours after the start of IMP administration and for at least 72 hours after the end of the SAR440234 infusion for signs and symptoms of tumor lysis, including serum creatinine, potassium, magnesium, phosphorous, calcium, and uric acid.
- Complete blood counts including white blood cell differential and ANC will be assessed daily during Cycle 1, the first 2 weeks of Cycle 2, and weekly thereafter for the duration of the treatment. Patients who develop Grade 3 or Grade 4 febrile neutropenia should receive broad spectrum antimicrobial therapy according to the hospital site's protocol. SAR440234 treatment should be discontinued for Grade 4 febrile neutropenia. Transfusion with red blood cells and platelets should be provided as needed.
- The study will be conducted at a limited number of sites, which will be selected based on their experience with potent immune modulating agents, treatment of leukemia, and CRS. Appropriate training will be provided, and the sites will be closely monitored.

The product is intended to be administered by IV infusion after reconstitution and dilution of lyophilized drug product in single use vials. While designing the strategy to ensure accuracy and control of the actual dose administered in each dose level, the following factors were considered: the extremely low starting dose, the wide range of doses expected during the dose escalation, the high potency of SAR440234, the risk of CRS, and the intended concentration of drug product formulation proposed for the FIH study. Hospital sites will be selected based on their demonstrated experience in complex administration procedures. Training will be reinforced at the sites, and procedures specified to minimize the risk of human error during dilution and potential product adsorption during drug preparation and infusion. The clinical administration protocol guidelines have been developed accordingly.

A solution for coating is supplied with SAR440234 that is used to coat infusion bags prior to dilution, which prevents adsorption of SAR440234 onto bags and infusion materials.

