- a **Evaluation:** Assessments should be performed prior to administration of SAR440234 (end of the previous cycle) unless otherwise indicated, at the end of the patient's participation in the trial, and at follow-up. Results should be reviewed by the Investigator prior to the administration of the next dose. If the patient is unable to attend monthly study visits, the investigator must obtain study follow up information via telephone call and record review from the patient's treating physicians.
- b End of treatment (within 30 days after the last administration of SAR440234): Obtain end of treatment assessments. If the patient does not plan to return for an EOT visit, the EOT evaluation must be performed on the day that the decision is made that the patient will not continue SAR440234.
- c **Post-study follow-up** for disease status, IMP-related AEs, and SAEs: Patients without documented disease progression at the end of a treatment visit who have not yet started treatment with another anti-cancer therapy will proceed with monthly follow-up visits until initiation of another anti-cancer therapy, disease progression, study cut-off date, or death. If the patient is unable to attend monthly study visits, the investigator must obtain study follow up information via telephone call and record review from the patient's treating physicians.
- d Day 1: Cycles run consecutively so that Day 1 of each cycle is normally 7 days after the start of the last infusion in the previous cycle.
- e Bone marrow aspiration will be performed for morphology (% of blasts) on Day 42 (±2 days) of Cycle 2 for evaluation of disease status. Subsequent bone marrow aspirates will be performed when clinically indicated, or if any of the following occurs: decreased neutrophil count Grade 4, decreased platelet count Grade 4, febrile neutropenia Grade 3 and Grade 4, anemia Grade 4 occurs with onset in >14 days before or after Day 42.
- f Flagged assessments: Cycle 2 only. Not required during Cycle 3 and subsequent cycles unless clinically indicated.
- g Blood hematology: Daily during Week 1 of Cycle 2, then weekly thereafter (on IMP administration days and on Day 42). Hemoglobin, hematocrit, white blood cell count with differential, percentage of blasts, platelet count.

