# Amended Clinical Trial Protocol 03 TED15138

29-Aug-2019 Version number: 2

- n **Blood chemistry:** Liver tests: SGOT (AST), SGPT (ALT), GGT, total bilirubin, direct bilirubin, AP. Renal function tests and electrolytes: Sodium, potassium, calcium, magnesium, phosphorus, bicarbonate, BUN, creatinine, and estimated creatinine clearance (Cockcroft-Gault formula), uric acid. Others: LDH, albumin, and total protein. Patients should be monitored every 8 hours after the start of drug administration and for at least 72 hours after the end of infusion for signs and symptoms of tumor lysis: serum creatinine, potassium, calcium, magnesium, phosphorus, and uric acid. Blood chemistry will also be rechecked 8 hours or less prior to each administration of SAR440234.
- o Serum or urine pregnancy test: Women of childbearing potential must have a negative serum or urine pregnancy test result at the end of study evaluation (Day 30 of the last cycle).
- p Urinalysis: Dipstick for pH, protein, glucose, at baseline, then as clinically indicated and at EOT.
- q Plasma cytokines (including interleukin-6 and interferon-γ): will be collected at the time points specified in the pharmacokinetic, pharmacodynamic, biomarker and immunogenicity flowcharts. An additional sample will be taken at onset of CRS Grade ≥2 if it occurs, or as soon as it is diagnosed.
- r Serum CRP/ferritin: will be collected at the same time points as cytokines.
- s SAR440234 administration: Systematic prophylactic premedication with dexamethasone 20 mg IV 4 and 1 hour prior to infusion of SAR440234 and montelukast 10 mg oral (PO) 4 hours prior to infusion are required. Dexamethasone 20 mg IV must be repeated 5 hours after the start of infusion if CRS Grade 2 has occurred in a previous patient or previous administration in the same patient. Specific instructions for the preparation and administration of SAR440234 are provided in the Pharmacy Manual.
- t Hospitalization: During Cycle 2, if the patient has tolerated the SAR440234 infusion during Cycle 1, the patient will be hospitalized only for the duration of each subsequent infusion (1 to 19 hours).

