# 6.7.2 Tumor Lysis Syndrome (TLS)

Blood chemistry (creatinine, potassium, calcium, magnesium, phosphorus, and uric acid) will be monitored every 8 hours for 72 hours after start of infusion to monitor for tumor lysis. If it occurs, appropriate treatment will be initiated that will include correction of serum calcium, potassium, or phosphorus abnormalities, and treatment of hyperuricemia with allopurinol and/or rasburicase, as indicated in Appendix J (35).

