# 12 STUDY PROCEDURES

#### 12.1 VISIT SCHEDULE

During the course of the study, all patients entering the study must be evaluated according to the schedule outlined in the flow charts in Section 1.2 (overall assessments), Section 1.3 (pharmacokinetic, pharmacodynamics, biomarker, and immunogenicity assessments) and described below. The results of the evaluation will be recorded in the eCRF pages until the patient is not followed anymore.

During the Dose Escalation Part of the study, patients must be hospitalized as indicated below:

- Cycle 1 for DL1 and DL2: for the duration of the SAR440234 infusion (1 to 19 hours) and for 72 hours after completion of each infusion, for safety monitoring.
- Cycle 1 for DL ≥3: for the duration of the SAR440234 infusion (1 to 19 hours) and for 72 hours after completion of each infusion, for safety monitoring. In Week 1 only, patients will receive an infusion of SAR440234 on Day 4. Therefore, patients in DL ≥3 will be hospitalized continuously from Day 1 of Week 1 until 72 hours after completion of the third infusion, ie, for 11 days.
- Cycle 2 for all dose levels: for the duration of the SAR440234 infusion (1 to 19 hours) and for 72 hours after completion of each subsequent infusion in Week 1 and Week 2 only, for safety monitoring. Hospitalization for all the other infusions is on the day of infusion only.
- Cycle 3 and beyond for all dose levels: on the day of infusion, only.

During the Expansion Part of the study, patients will be hospitalized as indicated below:

- Cycle 1 if the RP2D is DL1 or DL2: for the duration of the SAR440234 infusion (1 to 19 hours) and for 72 hours after completion of each subsequent infusion, for safety monitoring.
- Cycle 1 if the RP2D is DL ≥3: for the duration of the SAR440234 infusion (1 to 19 hours) and for 72 hours after completion of each subsequent infusion, for safety monitoring. In Week 1 only, patients will receive an infusion of SAR440234 on Day 4. Therefore, patients in DL ≥3 will be hospitalized continuously from Day 1 of Week 1 until 72 hours after completion of the third infusion, ie, for 11 days.
- Cycle 2 and beyond for all dose levels: on the day of infusion only.

If a subsequent treatment cycle is delayed for  $\geq 10$  days, treatment should resume with the lead-in doses, and the hospitalization guidelines for a first cycle of treatment must be applied.

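### The protocol contradicts itself on three safety-monitoring rules: Expansion Cycle 2 hospital stay, Cycle 2 blood counts, and the 72-hour tumor lysis window

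*Protocol*

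**What the plan says.** **Expansion hospitalization, Cycle 2.** Section 4.6, in its list of safety monitoring and risk mitigation measures, states: "During Cycle 1 and the first 2 infusions of Cycle 2 in the Expansion Part, patients will be hospitalized". It sets the length of that stay as "for the duration of the SAR440234 infusion (1 to 19 hours), and for 72 hours after completion of each infusion". Section 12.1, under the Expansion Part, states: "Cycle 2 and beyond for all dose levels: on the day of infusion only". Flow chart 1.2.4, footnote t, gives a third rule. On condition that the patient tolerated the Cycle 1 infusion, "the patient will be hospitalized only for the duration of each subsequent infusion (1 to 19 hours"). The hospitalization row of that chart marks infusion days only.

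**Blood counts, Cycle 2.** Section 4.6 has complete blood counts "assessed daily during Cycle 1, the first 2 weeks of Cycle 2, and weekly thereafter". Flow chart 1.2.4, footnote g, has "Daily during Week 1 of Cycle 2, then weekly thereafter". Footnote g of flow chart 1.2.2 (Dose Escalation) and section 12.5 agree with flow chart 1.2.4.

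**Tumor lysis checks.** Section 4.6 has 8-hourly checks in the first cycle, beginning at the start of administration and continuing "for at least 72 hours after the end of the SAR440234 infusion". The blood chemistry footnotes of flow charts 1.2.1 and 1.2.3 and section 12.4 give the same rule. Section 6.7.2 instead has "every 8 hours for 72 hours after start of infusion", and Appendix J also counts its 72 hours from the start of infusion.

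**The concern.** Section 4.6 argues that the risk of a first-in-human T-cell engager is acceptable partly because of the monitoring it lists. It names severe cytokine release syndrome and cytopenias as anticipated risks. Section 12.1 requires patients to be evaluated according to the flow charts. A site that follows the flow charts and section 12 would therefore not deliver two of the measures as section 4.6 describes them: the 72-hour stay for the first two Expansion Cycle 2 infusions, and the second week of daily counts.

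The tumor lysis conflict has a different shape. There the schedule and section 4.6 agree, and the safety-management text is the outlier. It still matters, because section 10.2 sends readers to section 6.7 for safety instructions, and that is where the shorter window stands.

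The protocol contains no rule saying which section prevails.

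**Working it through.** No sample size, power or error rate enters here, and the plan gives no figure to reproduce. The check sets the passages side by side and sizes each gap by simple arithmetic.

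**1. Hospital stay after the first two Expansion Cycle 2 infusions**

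- Section 4.6: infusion plus 72 h, for 2 infusions. Post-infusion stay = 2 x 72 = 144 h.
- Section 12.1: infusion day only, with no 72-hour stay after the infusion and no condition attached.
- Flow chart 1.2.4, footnote t: infusion only if Cycle 1 was tolerated, so 0 h for those patients. The footnote does not say what applies otherwise.
- Gap: up to 144 h per patient reaching Cycle 2. At most 37 patients are affected, the planned Expansion size; those who stop in Cycle 1 are not.
- Cross-check in Dose Escalation: section 4.6, flow chart 1.2.2 (footnote t) and section 12.1 all give 72 h after the first two Cycle 2 infusions. The conflict is confined to the Expansion Part.
- Knock-on: flow chart 1.2.4, footnote n, still asks for 8-hourly chemistry until at least 72 h after the end of infusion, and the chart marks chemistry on Days 2 to 4 and 9 to 11 of Cycle 2. Sampling every 8 hours is hard to carry out on a patient who goes home on the infusion day.

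**2. Blood counts in Weeks 1 and 2 of Cycle 2, both parts**

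- Section 4.6: daily on Days 1 to 14 = 14 counts.
- Flow charts 1.2.2 and 1.2.4 (footnote g) and section 12.5: daily on Days 1 to 7, then weekly on infusion days, so Day 8 is kept. 7 + 1 = 8 counts.
- Gap: 14 - 8 = 6 counts, on Days 9 to 14.

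**3. Tumor lysis window, with infusions of 1 to 19 h**

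- Section 4.6, flow charts 1.2.1 and 1.2.3, and section 12.4: the window ends at least (infusion length + 72) h after the start. Shortest infusion: 1 + 72 = 73 h. Longest: 19 + 72 = 91 h.
- Section 6.7.2 and Appendix J: the window ends 72 h after the start.
- Gap: 73 - 72 = 1 h to 91 - 72 = 19 h.
- In 8-hourly checks: 72/8 = 9 under section 6.7.2 and Appendix J. Covering the longer window takes 73/8 = 9.1, so 10 checks, up to 91/8 = 11.4, so 12 checks.

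**The case against.** The strongest reply is that section 4.6 is rationale, while the flow charts and section 12 govern conduct. On the first two points those sections direct sites away from section 4.6, so practice need not vary much. That has weight: the documents do not show that adverse-event detection would differ between sites, and this point does not claim it. It does not remove the contradiction, because section 4.6 states what will be done and presents it as risk mitigation.

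Three stronger readings are tempting and should be set aside.

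- A reader might infer that the 72 hours after an Expansion Cycle 2 infusion go unmonitored. They do not. Flow chart 1.2.4 keeps chemistry and vital signs on Days 2 to 4 and 9 to 11, with vital signs as clinically indicated at least until 72 h from the start of infusion. What differs is the inpatient stay, and footnote t shortens it only for patients who tolerated Cycle 1.
- A reader might infer that the visit schedule fails to deliver the tumor lysis monitoring of section 4.6. The Cycle 1 flow charts and section 12.4 match section 4.6, so a site on the schedule loses nothing. The 1 to 19 h shortfall arises only where section 6.7.2 or Appendix J is followed instead.
- A reader might infer an effect on the maximum tolerated dose. The first two conflicts concern Cycle 2, whereas dose-limiting toxicities are assessed over the 42 days of Cycle 1, and the Dose Escalation stay is consistent throughout.

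Section 4.6 also lists several other measures, so the benefit-risk case does not rest on these three alone.

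**Conclusion.** The protocol contradicts itself on three monitoring rules. None of the conflicts comes from redaction or from superseded text.

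- Expansion Cycle 2 stay: up to 144 h of inpatient observation per patient reaching Cycle 2, with three different rules in three places and an 8-hourly chemistry requirement that fits poorly with an infusion-day stay.
- Cycle 2 blood counts: six counts (Days 9 to 14), in both parts.
- Tumor lysis window: 1 to 19 h, with section 6.7.2 and Appendix J against section 4.6, the Cycle 1 flow charts and section 12.4.

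These sizes assume infusions within the stated 1 to 19 h and, for the stay, that the patient receives both Cycle 2 infusions and is discharged as section 12.1 or footnote t allows. The SAP (sections 4.3 and 4.9) records early termination of the trial, which limits the practical effect on the Expansion Part. The count conflict also covers Dose Escalation, and section 6.7.2 is not confined to either part. The correction is worth making because it concerns patient safety, although no analysis result is shown to change.

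**What to change.** Reconcile section 4.6, section 6.7.2, section 12.1, section 12.5, Appendix J and flow charts 1.2.1 to 1.2.4 so that each point has one rule, stated identically everywhere:

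- the Expansion Cycle 2 stay, including whether tolerance of Cycle 1 is a condition, and how the 8-hourly chemistry in flow chart 1.2.4, footnote n, is to be done under the stay given in footnote t;
- how far into Cycle 2 daily blood counts continue;
- whether the 72-hour tumor lysis window is counted from the start or the end of infusion.

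The sponsor decides which rule stands in each case. If a measure in section 4.6 is not retained, the benefit-risk text should be revised to describe what sites will actually do. The cost of the reconciliation itself is protocol wording.

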# 6.2.1 Starting dose and dose levels

SAR440234 will be administered IV on Day 1, Day 4 (DL≥3), Day 8, and weekly thereafter in Cycle 1 for a 42-day cycle. The dosing regimen will be weight-based; however, if a patient weighs >140 kg, the patient's weight will be capped at 140 kg for dose calculations. The administration of the investigational medicinal product (IMP) will begin at the selected safe starting dose for an FIH trial, based on the MABEL, and by integration of all available in vivo and in vitro data at the start of the study.

A 3+3 dose escalation scheme will be used, based on DLTs observed during the first 42 days following the first administration of IMP in the first cycle (the DLT observation period). The goal is to treat 3patients per dose level in order to follow a 3+3 design. In this FIH study, potential DLTs are defined as the following:

• Any Grade ≥3 nonhematological AE, unless either caused by disease progression or an obviously unrelated cause or caused by a laboratory abnormality without associated clinical consequences that resolves within 5 days (AE's related to cytopenias that were present prior to starting SAR440234 or to underlying leukemia will not be considered DLT's).

- Grade 4 hematological toxicities as defined in NCI-CTCAE v4.03, ie, new onset or
  worsening of life-threatening hematological abnormalities after administration of
  SAR440234 (AE's related to cytopenias that were present prior to starting SAR440234 or
  to underlying leukemia will not be considered DLT's).
  - Grade 4 bone marrow hypocellularity, if not caused by disease progression and not improved to baseline value or Grade ≤1 within 14 days,
  - Grade 4 decreased neutrophils, if not present at baseline and not resolved to baseline value or Grade ≤1 within 14 days,
  - Grade 4 febrile neutropenia not resolved within 7 days,
  - Grade 4 decreased platelet count, if not present at baseline and not improved to baseline value or Grade ≤1 within 14 days,
  - Grade 4 anemia, if not improved to baseline value or Grade ≤1 within 14 days.
- Grade 3 or Grade 4 CRS.
- Grade 2 CRS if it persists for >48 hours or is present <48 hours before the time when the next planned dose of SAR440234 is due.
- Any treatment-emergent adverse event (TEAE) that, in the opinion of the Principal Investigator and Sponsor, is of potential clinical significance such that further dose escalation would expose patients to unacceptable risk.

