### 6.3 MAXIMUM ADMINISTERED DOSE / MAXIMUM TOLERATED DOSE

The dose escalation will end when the MAD is reached, which will be defined as the dose at which ≥33% of evaluable patients have experienced an IMP-related DLT during the DLT observation period in a cohort of 6 patients.

The MTD will be defined as the highest dose level at which no more than 1 patient of a maximum of 6 patients experienced an IMP-related DLT.

The patient population evaluable for MTD determination in the Dose Escalation Part will consist of all patients who receive at least 5 out of 6 weekly IV administrations of SAR440234 in DL1 and DL2, patients who receive at least 6 out of 7 IV administrations of SAR440234 in DL  $\geq$ 3, and patients who discontinue the IMP before completion of Cycle 1 because of a DLT.

A patient who discontinues the IMP before the end of the DLT observation period or does not receive the planned dose for any reason other than DLT, will be replaced by enrolling another patient. The first 3 patients treated during the Dose Escalation Part of TED15138 will be replaced. Another 3 patients will be enrolled in DL1 and the trial will proceed according to the 3+3 design.

The dose level below the MAD will be considered the preliminary MTD, providing DLTs are observed in fewer than 2 of 6 treated patients (or fewer than one-third if more than 6 patients) at that dose level. Intermediate dose levels may be evaluated according to Study Committee recommendations. The MTD is generally the highest dose level at which at most 1 patient of a dose level cohort experiences a DLT.

Although the dose escalation process is guided by the safety evaluation during the DLT observation period, cumulative or irreversible toxicities observed in subsequent administrations should also be considered for the dose escalation and dose selection decisions (ie, smaller increases in dose, expansion of a given dose level, or an intermediate dose level), upon agreement between the participant Investigators and the Sponsor.

In the absence of an MTD, pharmacokinetic and pharmacodynamic parameters may help to define the recommended dose of SAR440234 to be tested in the expansion cohort part of the study.

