# Decreased neutrophil count Grade 4, decreased platelet count Grade 4, or febrile neutropenia Grade 3 and Grade 4, and anemia Grade 4:

- If the AE resolves before the time of the next schedule infusion or within ≤10 days after the last infusion, treatment will be given as planned after recovery with dose reduction by 1 step.
- If the AE resolves in 10 to 14 days after the last infusion, omit 1 dose. After recovery, treatment will resume with dose reduction by 1 step, and will restart with the lead-in dose.
- If the AE persists >14 days after the last infusion, a bone marrow aspirate will be performed.
  - If <3 infusions of SAR440234 have been administered, the study treatment will be permanently discontinued,
  - If ≥3 infusions of SAR440234 have already been administered, the patient will resume the study treatment, once the AE has resolved, if there is perceived benefit, and the Investigator and Sponsor agree. Dose reduction by 1 step must be applied, and treatment will resume with the lead-in dose.

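### Grade 4 febrile neutropenia: Section 4.6 calls for discontinuation without conditions, while Section 6.5.4 and Table 7 mostly have treatment go on at a reduced dose; DLT evaluability is affected in a limited set of cases

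*Protocol*

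**What the plan says.** **Section 4.6**, in its list of safety monitoring and risk mitigation measures, states: "SAR440234 treatment should be discontinued for Grade 4 febrile neutropenia". It sets no condition on duration, cause or number of infusions.

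**Section 6.5.4** has a block whose title includes "or febrile neutropenia Grade 3 and Grade 4, and anemia Grade 4". Its branches are:

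- Resolved before the next scheduled infusion or within 10 days of the last one: "treatment will be given as planned after recovery with dose reduction by 1 step".
- Resolved somewhat later: "If the AE resolves in 10 to 14 days after the last infusion, omit 1 dose", after which treatment resumes one step lower, starting with the lead-in dose.
- Persisting beyond 14 days: "If <3 infusions of SAR440234 have been administered, the study treatment will be permanently discontinued". Otherwise, "If ≥3 infusions of SAR440234 have already been administered, the patient will resume the study treatment, once the AE has resolved", provided benefit is perceived and the Investigator and Sponsor agree.

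Table 7 repeats this scheme. Its footnote lets treatment go on after a mandated permanent stop if there is clinical benefit, the event has resolved, and both parties agree. The opening of 6.5.4 also lets dosing continue unchanged when the event is attributed to the malignancy or baseline cytopenias and both parties consider that safe.

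**Section 4.5.3** says that for Grade 3 or 4 hematological toxicity the dosing interval is to be extended until resolution.

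**DLT rules.** Section 6.2.1 lists as a DLT "Grade 4 febrile neutropenia not resolved within 7 days". Section 13.3.2 and SAP Table 3 define a DLT-evaluable patient by number of administrations (at least 5 of 6 in DL1 and DL2, at least 6 of 7 from DL3), or by stopping early because of a DLT. Under Section 6.3, a patient who stops within the observation period, or does not get the planned dose, for a reason other than DLT "will be replaced by enrolling another patient".

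**The concern.** The event is Grade 4, in a first-in-human study that is restarting after a full clinical hold. An investigator reading 4.6 would stop the drug. One reading 6.5.4 would, in most situations, give it again at a lower step. Both would be following the current protocol.

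The statistical interest is that the dosing action feeds the 3+3 data. Cohorts are 3 or 6 patients, so whether one patient counts or is replaced concerns a third or a sixth of the evidence for an escalation decision. If the action depends on which section a site read, the DLT-evaluable population depends on it too.

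**Working it through.** No stated figure in the plan depends on this point, so there is none to reproduce. The check has three steps.

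**1. The two dosing rules side by side, for Grade 4 febrile neutropenia**

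| Course of the event | Section 4.6 | Section 6.5.4 and Table 7 |
|---|---|---|
| Resolved within 10 days of last infusion | Discontinue | Continue, 1 step lower |
| Resolved later, up to day 14 | Discontinue | Omit 1 dose, then lead-in, 1 step lower |
| Beyond 14 days, at least 3 infusions given | Discontinue | Resume once resolved, if benefit and agreement; lead-in, 1 step lower |
| Beyond 14 days, fewer than 3 infusions given | Discontinue | Permanent discontinuation, subject to the Table 7 footnote |
| Attributed to disease or baseline cytopenias, agreed safe | Discontinue | Continue unchanged |

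The rules coincide in one row of five, and there only if the footnote is not invoked. Section 4.5.3 (lengthen the interval) matches neither column throughout.

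**2. DLT evaluability when the event is not a DLT**

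Let P be the planned Cycle 1 administrations (6 in DL1 and DL2, 7 from DL3), and k the number given before onset. By Section 13.3.2 the patient is evaluable if administrations given ≥ P − 1.

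- Under 4.6, given = k. For P = 6 the threshold is 5, so k = 1 to 4 fails and k = 5 or 6 passes. For P = 7 the threshold is 6, so k = 1 to 5 fails and k = 6 or 7 passes.
- Under 6.5.4, with 0 or 1 dose omitted, given = P or P − 1. That is 6 or 5 of 6, or 7 or 6 of 7, and all of these pass. This assumes that every other planned Cycle 1 infusion is given.

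Evaluability can therefore differ only for onset after doses 1 to 4 of 6 or 1 to 5 of 7. If the event lasts more than 7 days and is a DLT, the patient is evaluable under either rule and nothing changes.

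**3. Replacement**

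- A patient stopped under 4.6 at one of those values of k is not evaluable and is replaced (Sections 6.3, 11.2 and 13.1.1).
- A patient continued under 6.5.4 after a dose reduction is evaluable on the count of administrations. Section 6.3 nevertheless replaces anyone who did not receive the planned dose for a non-DLT reason. Section 11.2 and SAP Section 2 do the same for anyone not treated as planned. A 1-step reduction arguably meets both descriptions. Section 13.1.1 and SAP Table 3 mention only discontinuation as the ground for replacement.
- A patient continued unchanged, because the event is attributed to disease or baseline cytopenias, is not dose-reduced, so the planned-dose clause is not triggered.

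**The case against.** The strongest reply is that the protocol shows where dosing rules live. Section 6.5 says that delays, omissions and modifications for adverse events are set out in 6.5.3 to 6.5.5, and Section 6.7.3 refers hematological toxicity to 6.5.4. Section 4.6 is a summary in the rationale chapter. Appendix K also records that Amendment 01 removed discontinuation text for Grade 3 febrile neutropenia and Grade 4 marrow hypocellularity because it did not match 6.5.4. This lowers the practical risk. It does not remove the conflict: no clause gives 6.5.4 precedence, 4.6 presents its sentence as part of the risk mitigation plan, and Section 11.1.1 does not name the event either way.

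The reply is also right to limit some stronger readings:

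- A reader might infer that 4.6 mandates permanent discontinuation. It says *should* and omits *permanently*, a word the protocol uses elsewhere when it means that. An unconditional stop is still its plain reading.
- A reader might infer that 6.5.4 always leads back to treatment. One branch ends it. Section 6.5.2 also ends treatment when a reduction is needed after a certain dose, which is redacted.
- A reader might infer a clean contrast, replaced under 4.6 and evaluable under 6.5.4. Sections 6.3 and 11.2 blur this for any dose-reduced patient.
- An event that clears within 7 days can still be called a DLT under the clinical-significance item in 6.2.1. In that case evaluability does not differ.

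**Conclusion.** The inconsistency between Section 4.6 and Section 6.5.4 with Table 7 is real, lies in current text and concerns patient safety. Section 4.5.3 adds a third wording. This is the main point, and it applies wherever the protocol's dosing rules apply.

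The effect on the 3+3 data is secondary and bounded: Cycle 1 of the Dose Escalation Part, an event not counted as a DLT, and onset after doses 1 to 4 of 6 or 1 to 5 of 7. Within those bounds one patient's status is at issue, which is 1 of 3 or 1 of 6 in a cohort. The documents give no expected frequency for the event, so neither the number of patients affected nor the effect on escalation decisions can be estimated.

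A reader might infer that every patient with Grade 4 febrile neutropenia alters the DLT denominator, or that the Expansion Part's two-stage design is compromised. The documents support neither. Later onset and DLT-qualifying events leave evaluability unchanged, and the Simon design does not use DLT evaluability.

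The evaluability result assumes that all remaining Cycle 1 infusions are given apart from at most one omission, and that administrations at a reduced or lead-in dose count toward the threshold, since Section 13.3.2 counts administrations without reference to dose.

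**What to change.** 1. Reconcile Sections 4.5.3, 4.6, 6.5.4 and Table 7 so that sites have one instruction for Grade 4 febrile neutropenia. Which clinical rule applies is for the sponsor to decide.
2. Align the replacement wording in Sections 6.3 and 11.2 (and SAP Section 2) with the definitions in Section 13.3.2 and SAP Table 3. State whether a patient who is dose-reduced for a non-DLT event stays in the DLT-evaluable population or is replaced.

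The cost is protocol wording with a matching SAP edit. No sample size, boundary or data collection changes.
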